### **STATISTICAL CONSIDERATIONS:**

Primary goal of this study is to assess the benefit of zinc supplementation by increasing zinc levels and hence improving several important biomarkers. To assess the effect of supplementation and its' positive influence on markers of inflammation and immune activation known to be associated with HIV-comorbidities, 95 HIV+ subjects (see below for the sample

size justification) will be studied for 6 months from the available HIV+ subjects pool. During this period outcome variables (primarily, zinc levels and sCD14) and biomarkers will be measured at baseline (0), 6, 12, 18, and 24 weeks. The outcome variables will be analyzed, and predicted values will be portrayed longitudinally. The main outcome variables zinc levels and sCD14 are continuous variables. Therefore, linear mixed model and likelihood ratio test will be used in testing hypotheses (see details below).

The HIV+ subjects in the supplementation arm will take 90 mg elemental zinc daily for 24 weeks whereas the HIV+ subjects in control arm will take matching placebo. Both groups of subjects will be in the study for 24 weeks. Outcomes of the intervention will be measured longitudinally at baseline (0), 6, 12, 18 and 24 weeks as noted in the Schedule of Evaluations Table. These outcome variables are in continuous scale. Linear mixed-effects modeling will be used in analyzing these longitudinal measurements to understand their trajectories over the study period. We will collect information on the covariates demographics, lifestyle habits, dietary and socioeconomic factors, and HIV/ART factors. For reproducibility of the results, the data quality will be reviewed rigorously, and necessary transformations will be performed to satisfy assumptions related to residuals for parametric models. Basic descriptive statistics will be used to summarize outcomes and covariates within each group of subjects. We anticipate that the two groups will show some but not complete overlap in their distributions in terms of our baseline covariates. To depict the impact of supplementation, summary statistics as well as predicted values of longitudinally measured outcome variables will be presented graphically. Models for longitudinally measured outcome variables, analysis method, and computation of power are presented below. One-sided hypothesis tests are performed assuming a 0.10 level of significance (standard for phase II trial). The error rate in multiple comparisons will be controlled by the step-up Bonferroni correction procedure. The sample size estimation will be based to achieve power of 0.80.

**Aim 1&2:** we assess the benefit of the zinc supplementation in HIV+ patients. In these aims we will study the impact of zinc supplementation in increasing zinc levels and improving markers related to HIV-comorbidities. We will measure the outcome variables in two-groups at 5 times points during 6 months period. To delineate the outcomes over 6 months period, we will analyze the 6 months outcome data using a linear mixed-effects model. Let  $Y_{ij}$  denote an outcome variable from the  $i$ th subject at the  $j$ th week, where  $i=1, 2, \dots, 95$  HIV+ subjects;  $j=0, 6, \dots, 24$  weeks. Define  $T_{ij}$  to be the week when the response measurements are collected from subject  $i$ . A linear mixed model for the outcome  $Y_{ij}$  can be written as

$$Y_{ij} = \alpha + \beta_0^T X + \beta_1 I + \beta_2 T_{ij} + \beta_3 I \times T_{ij} + \nu_{0i} + \nu_{1i} T_{ij} + \varepsilon_{ij} \quad (1),$$

where  $X$ =vector of covariates,  $I$ =zinc supplementation (yes/no), the vectors of random effects  $\nu_i = (\nu_{0i}, \nu_{1i})'$  are assumed to be independent multivariate normal with mean vector 0 and covariance matrix  $G(\theta) = G(\sigma_{v11}, \sigma_{v12}, \sigma_{v22})$ . The error term  $\varepsilon_{ij}$  in model (1) is assumed to be distributed as normal  $(0, \sigma^2)$ . The  $\beta$ 's are fixed effects parameters, and  $G$  is assumed to be an unstructured covariance matrix. From the fitted model (1), we will delineate the predicted outcome variables, association between outcomes and zinc supplementation therapy. The model parameters will be estimated by the method of restricted maximum likelihood. Likelihood ratio tests will be used to compare overall mean curves for the two-group. Tests for inequality in 2-group at baseline (0), 6, 12, 18, and 24 weeks will be performed with multiple testing corrections using the Bonferroni correction procedure. Note that if there are large numbers of missing values in this longitudinal study, we will estimate the parameters by utilizing the "pattern

mixture model" which assumes model (1). In the case of parametric model assumption violation, we will consider using the generalized estimating equation approach; but this will be avoided, if possible, because it will lead to decreased power.

**Correlational analyses of the secondary and exploratory objectives:** To assess the associations of concurrently measured biomarkers, we will present descriptive statistics at each time point, plot the individual/group trajectory of changes, and apply bivariate linear mixed effects models ([14]). Here we use biomarker as a general term to indicate that it is a continuous variable from a statistical point of view. We will compute summary statistics (mean, median, SD, coefficient of variation, Cohen's d, etc.) for each biomarker, at each time point. We will plot these summary statistics over the study period for better understanding the trajectory of these biomarkers. Specifically, we will be presenting two biomarker summary statistics in each graph for better understanding the trajectory of one biomarker and its relationship with the other relevant biomarker: HOMA-IR vs. Zinc. We expect that an increasing trend in zinc should lead to a decreasing trend in HOMA-IR level. We will also plot the biomarkers at each time point using box plots. The box plots will depict a biomarker distribution at every time point (baseline, week 12 and 24). The box plots will give us an overall direction of change in the study population. Since our focus is in the treated group, we will present biomarker trajectories using spaghetti plots for examining individual changes. The spaghetti plots will help in determining analysis models. We will apply the bivariate linear mixed effects (BLME) model for studying evolving relationship in two biomarkers. The BLME model is an extension of equation (1), which allows jointly analyzing two biomarkers together. The BLME model will include random effects and/or first-order auto-regressive process, and independent measurement error for both biomarkers. The joint analyses will provide estimates of correlation coefficients among the biomarkers[14]. Again, for the correlational analysis our focus will be the treated group. The BLME model for Gaussian longitudinal biomarker data will be implemented in SAS MIXED procedure. For faster computational benefit, we will apply the Newton-Raphson algorithm, instead of EM algorithm.

**Sample Size and Power analysis:** The following sample size estimation and power analysis is based on the significance level 0.10 and 80% power. We hypothesize that after the zinc supplementation the HIV+ subjects will have higher levels of zinc and lower levels of sCD14. Based on our data from SATURN-HIV study, we assume that, at baseline/before the supplementation, the average  $\pm$  SD of log(sCD14) for all HIV+ subjects is  $7.66 \pm 0.32$ . Using Frison and Pocock's change method, we estimate the sample size based on the difference in the two groups of the mean change of the post-intervention measurements at month six from the baseline measurement, assuming that correlation between repeated measurements is 0.85. A mean difference of 0.08 ng/ml log(sCD14) change between two groups, 27 HIV+ subjects in the control arm and 54 HIV+ subjects in the intervention arm, in a longitudinal measures design with 5 longitudinal measurements can be detected with 80% power using a t-test. In this prospective longitudinal study we anticipate 15% subjects missing/non-compliance because of variety of reasons. Therefore, our final sample size estimates for the control and intervention arms are 31 and 62, respectively. The sample size estimation was performed using STATA 14.0.

**Effect size consideration:** As above, we previously stated that we will perform significance tests for the shift of distributions of biomarkers after the zinc supplementation using Kolmogorov-Smirnov (K-S) test. The amount of shift or effect size will be measured using Cohen's d value. For estimating the effect size, we used our statin study data as the preliminary

data (NCT01218802). In the statin study the baseline mean (SD) of hs-CRP, log(sCD14), log(sTNF-RI), and LBP are 4.95(10.45), 7.71 (0.35), 7.46 (0.37), and 21.11(10.91), respectively. For zinc supplementation (90 mg) we will compute the change in a biomarker by taking the difference of a biomarker measured before- and after- the zinc supplementation. For example, we will compute the difference in LBP measured at baseline and after the zinc supplementation. Similarly, differences will be computed for the other biomarkers. The effect size estimation is performed using nQuary Advisor 7.0 software.

All analysis will be by intent to treat. All subjects, regardless of whether they remain on study drug, will continue to be followed throughout the duration of the study. It is standard practice in the HIV studies where inflammation markers are measured, that every attempt would be made to schedule study visits during a time that subjects are not acutely ill. That would mean that a visit would be rescheduled if a patient shows up sick, as acute illnesses may affect inflammation markers. A period of >7 days ill-free would be required. This happens rarely overall but if it does in the setting of this study, participants would be asked to come back after illness resolves.

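### Model (1) gives the randomised arms separate baseline means and does not use the Entry marker value; sharing one baseline mean or adjusting for Entry is a free improvement

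*Combined protocol and SAP*

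**What the plan says.** All references are to the combined protocol and SAP.

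- **The model.** STATISTICAL CONSIDERATIONS, Aim 1&2, equation (1), has an intercept, a covariate vector X, an arm term β1·I, a time term, an arm-by-time term β3 and random intercepts and slopes. I is defined as "zinc supplementation (yes/no), the vectors of random effects" and so on. The week index starts at 0, so the baseline measurement is one of the outcomes and β1 is the between-arm difference before dosing.
- **The covariates.** "We will collect information on the covariates demographics, lifestyle habits, dietary and socioeconomic factors, and HIV/ART factors". The baseline value of the marker is not named. The section provides neither for a common baseline mean nor for analysis of covariance on the Entry value.
- **The tests.** Likelihood ratio tests compare the whole mean curves. Between-arm tests follow at each of weeks 0, 6, 12, 18 and 24 with a Bonferroni correction. No single contrast is named as the treatment effect.
- **The schedule.** The table under Design and Outcomes places the inflammation and immune activation markers, microbial translocation and zinc at Entry and weeks 12 and 24 (zinc also at Screen I). The paragraph on correlational analyses likewise lists baseline, week 12 and week 24. The statistical text speaks of five visits.
- **The sizing.** Sample Size and Power analysis uses the Frison and Pocock change method, "assuming that correlation between repeated measurements is 0.85", with this target: "A mean difference of 0.08 ng/ml log(sCD14) change between two groups, 27 HIV+ subjects in the control arm and 54 HIV+ subjects".
- **The overlap remark.** "We anticipate that the two groups will show some but not complete overlap in their distributions in terms of our baseline covariates".

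**The concern.** In a randomised trial the two arms have the same expected marker level before the first dose. A model that estimates that level separately in each arm discards this knowledge. Two things follow. The arm-by-time contrast is less precise than it could be from the same data. Also, whatever chance difference exists at Entry feeds into the estimate: slightly and with reversed sign for a change-type contrast, and almost in full for a comparison of the arms at week 24.

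The second consequence matters more because the plan does not say which quantity is the treatment effect. The visit-wise tests contain β1. If the test of whole curves covers β1 and β3 jointly, it too counts a baseline difference as effect. The week-0 test uses part of the multiplicity correction on a null hypothesis that randomisation already makes true.

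**Working it through.** **Inputs.** From Sample Size and Power analysis: SD of log(sCD14) 0.32, ρ = 0.85, difference 0.08, evaluable 54/27, final 62/31. From STATISTICAL CONSIDERATIONS: "One-sided hypothesis tests are performed assuming a 0.10 level of significance". Equal correlation between visits is assumed. Arm sizes are zinc/placebo.

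**1. The plan's own figure.** Control-arm n = 1.5 × (0.32/0.08)² × f × (zα + zβ)², where f = (1 + (r−1)ρ)/r + 1 − 2ρ for r post-baseline measurements. With r = 5, f = 0.88 + 1 − 1.70 = 0.18. With two-sided 0.10, (1.6449 + 0.8416)² = 6.183. Then n = 1.5 × 16 × 0.18 × 6.183 = 26.71, which gives 27 and 54 (power 80.4%). The final sizes are 27 × 1.15 = 31.05 and 54 × 1.15 = 62.1. The match is exact only with a two-sided test and five post-baseline measurements. With one-sided 0.10 the control arm is 25 for r = 2 and 33 for r = 1. The steps below use the one-sided 0.10 that the plan states.

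Under the variant that reproduces 27/54, adjusting for baseline replaces f by 0.88 − 0.85² = 0.1575. That needs 24 and 47 (71 against 81), or gives 84.8% power at 54/27.

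**2. What β3 is on the marker schedule.** With complete data at 0, 12 and 24 weeks, the fitted slope uses weights −1, 0, +1, so 24·β3 is the between-arm difference in change from Entry to week 24.

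**3. Precision, three visits.**
- Change: variance factor 2(1 − ρ) = 0.300.
- Entry-adjusted: 1 − ρ² = 0.2775.
- Ratio: (1 + ρ)/2 = 0.925, a 7.5% reduction.

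SE = 0.32 × √factor × √(1/n1 + 1/n2), and power = Φ(0.08/SE − 1.2816).

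| Arms | SE, change | Power | SE, Entry-adjusted | Power |
|---|---|---|---|---|
| 54/27 | 0.0413 | 74.4% | 0.0397 | 76.8% |
| 62/31 | 0.0386 | 78.6% | 0.0371 | 80.9% |

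Model (1) with β1 removed gives SE 0.0397 and 76.9% at 54/27, the same for practical purposes.

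**4. Precision, five visits.** If markers were measured at 0, 6, 12, 18 and 24 weeks, the SE of 24·β3 at 54/27 is 0.0370 under model (1) and 0.0358 with a common baseline mean. Power goes from 81.2% to 83.0%.

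**5. Carry-over into the change contrast.** The SE of the chance baseline difference at 62/31 is 0.32 × √(1/62 + 1/31) = 0.070. A one-SE difference shifts the three-visit change contrast by (1 − 0.85) × 0.0704 = 0.011 in the opposite direction, 13% of 0.08. With five visits the slope weights at the first and last visits are −0.8 and +0.8 and the shift is 0.8 × 0.15 × 0.0704 = 0.0084.

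**6. The week-24 comparison.** Under model (1) this is β1 + 24·β3. The observed week-24 difference carries ρ = 0.85 of a baseline difference. The fitted line on three visits has weights −1/6, 1/3, 5/6 at its end, so it carries −1/6 + 0.85 × 7/6 = 0.825. At 54/27 the SE of the baseline difference is 0.0754, so at 0.85 a one-SE difference moves the comparison by 0.064, or 80% of the target. The contrast's SE is 0.0745. Power is Φ(0.08/0.0745 − 1.2816), about 42%, before any Bonferroni correction.

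**7. Other markers.** The plan gives no correlation for hs-CRP, sTNF-RI, LBP or zinc. As an assumed range, the ratio (1 + ρ)/2 is 0.80 at ρ = 0.6 and 0.75 at ρ = 0.5.

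**The case against.** The best defence is that the plan is coherent. It sizes the trial by the change method, and a change-type contrast matches that. At the plan's own correlation the gain is 2 to 3 power points, so this is a recognised improvement and not the correction of an error. That stands, and it sets the weight of the point.

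The defence also holds against several stronger readings that a reader might infer:

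- *That the analysis is biased or invalid.* Over repeated randomisations the contrasts are unbiased. The carry-over is conditional on the imbalance that happens to occur.
- *That model (1) can never do better than a change score.* The identity in step 2 needs three equally spaced visits and complete data. On the five visits in the statistical text, model (1) has SE 0.0370, below both the change score (0.0413) and week-24 analysis of covariance (0.0397). The schedule supports three visits for the markers, but the plan is not consistent on this.
- *That the Entry value is excluded.* X is left open, and the covariate sentence lists what will be collected. The Entry value is simply not named, and using it as a covariate would sit awkwardly with week 0 as an outcome.
- *That the overlap sentence shows the defect.* It concerns baseline covariates in a descriptive context. The defect lies in equation (1).

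What the defence does not answer is that the plan never names β3 as the effect, and that the week-24 tests it does plan are far weaker than the change contrast on which the trial was sized.

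**Conclusion.** The point holds as a free improvement and does not threaten validity. For sCD14, under ρ = 0.85, SD 0.32, difference 0.08, one-sided 0.10, complete data and equal correlation between visits, the gain on the arm-by-time contrast is 2 to 3 power points on the marker schedule and just under 2 points if all five visits carried the marker. If the test were two-sided at 0.10, three-visit power at 54/27 would go from 61.5% to 64.5% with a common baseline mean. The gain would be larger for any marker with a lower correlation, but the documents give no figure, so the ratios at 0.5 and 0.6 are assumptions. The larger practical gain is in interpretation. If the week-24 between-arm test of model (1) were taken as the result, its power would be about 42% and most of a chance Entry difference would appear in it.

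**What to change.** In STATISTICAL CONSIDERATIONS, Aim 1&2:

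1. Remove β1·I from model (1) so that both arms share one baseline mean (constrained longitudinal model). Alternatively, model only the post-baseline visits with the Entry value of the same marker as a covariate.
2. Name the week-24 between-arm contrast from that model as the treatment effect for each co-primary marker.
3. Remove the week-0 between-arm test from the list of tests and from the multiplicity correction. It has no meaning once the baseline means are shared. With a plain Bonferroni split over the five listed weeks, the per-test level would move from 0.10/5 = 0.02 to 0.10/4 = 0.025.

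Deleting the sentence on incomplete overlap is optional and changes no analysis.

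The cost is wording only. Entry values of the co-primary markers are already scheduled, so no visit, sample or participant is added and no power is lost. The change should be made before unblinding, so that the choice among change, week-24 and whole-curve tests is not left until results are known.

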## **STUDY OBJECTIVES**

### **PRIMARY:**

- To replicate findings from R21 and examine whether zinc supplementation will change biomarkers (hs-CRP, sCD14, sTNF-RI, and LBP)
- To examine whether zinc is safe and effective at increasing zinc levels in HIV-infected subjects with zinc deficiency

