## **STUDY ENDPOINTS**

### **Co-PRIMARY:**

--Changes in markers of inflammation and immune activation: hs-CRP, sCD14, sTNF-RI and microbial translocation LBP)

-Changes in zinc levels (before and after supplementation)

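### The primary endpoint list differs between sections (five variables or two), the step-up Bonferroni rule names no family or success rule, and the 80% power covers log(sCD14) alone with contrast and sidedness left unclear

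*Combined protocol and SAP*

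**What the plan says.** **Endpoints.** Under Co-PRIMARY, in both the Précis and the Study Endpoints section, the plan lists "Changes in markers of inflammation and immune activation: hs-CRP, sCD14, sTNF-RI and microbial translocation LBP" and, as a second bullet, "Changes in zinc levels (before and after supplementation". That is five variables under two bullets. The primary objective also covers all four markers: to "examine whether zinc supplementation will change biomarkers (hs-CRP, sCD14, sTNF-RI, and LBP". Statistical Considerations is narrower: "The main outcome variables zinc levels and sCD14 are continuous variables".

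**Error control.** The same section states "One-sided hypothesis tests are performed assuming a 0.10 level of significance", and then: "The error rate in multiple comparisons will be controlled by the step-up Bonferroni correction procedure". No list of hypotheses follows. Under Aim 1&2, "Likelihood ratio tests will be used to compare overall mean curves for the two-group"; after that, "Tests for inequality in 2-group at baseline (0), 6, 12, 18, and 24 weeks will be performed with multiple testing corrections", by plain Bonferroni. The plan does not say how this second correction relates to the step-up rule.

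**Power.** Sample Size and Power analysis works at 0.10 without stating sidedness, and considers log(sCD14) only. It describes the change from baseline at month six but also refers to five longitudinal measurements. It arrives at 27 control and 54 intervention subjects for 80% power. Zinc has no effect size or power there. hs-CRP, sTNF-RI and LBP have only baseline means and SDs.

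**Visits.** The Précis schedule, the Week 12 and 24 procedures and the correlational-analyses text place marker values after baseline at weeks 12 and 24. Statistical Considerations says outcomes are also measured at weeks 6 and 18, where the visit procedures only store samples for possible later testing.

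**The concern.** A step-up procedure is undefined until its family is fixed, because each p-value is compared with a limit that depends on how many hypotheses there are and how the others turn out. Here the family could be two or five, depending on which section is followed, and either choice could be defended after the results are known. The Study Design section calls this the confirmatory phase, so calling it a pilot does not remove the need for a defined success rule.

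Co-primary is also left undefined. If any one success is enough, the family must be named and alpha shared. If all must succeed, no alpha is split, but joint power becomes the relevant quantity and the plan gives none. The stated 80% describes neither case: it is the power of a single endpoint with no split, and it does not match the month-six contrast combined with the stated one-sided test.

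**Working it through.** **1. Does the family change the result?** Read step-up Bonferroni as Hochberg's procedure (an assumption; the plan gives no formula). Take zinc p < 0.001, sCD14 one-sided p = 0.06, and the other three p > 0.10.
- Family of two: the larger p-value, 0.06, is compared with 0.10. sCD14 succeeds.
- Family of five: the three largest exceed 0.10 and so miss their limits of 0.10, 0.05 and 0.033. sCD14 is then compared with 0.10/4 = 0.025 and fails.

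**2. Reproducing 27/54.** Inputs from Sample Size and Power analysis: SD 0.32, correlation 0.85, difference 0.08, allocation 1:2. For the mean of k follow-ups minus baseline, the change method gives

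variance = 0.32² × [(1 + (k − 1) × 0.85)/k + 1 − 2 × 0.85]

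SE = √[variance × (1/27 + 1/54)], and power = Φ(0.08/SE − z).

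| k | Variance | SE | One-sided 0.10 | Two-sided 0.10 (= one-sided 0.05) |
|---|---|---|---|---|
| 1 (month six) | 0.03072 | 0.0413 | 74.4% | 61.5% |
| 2 (weeks 12, 24) | 0.02304 | 0.0358 | 83.0% | 72.3% |
| 4 | 0.01920 | 0.0327 | 87.9% | 78.9% |
| 5 | 0.01843 | 0.0320 | 88.8% | 80.4% |

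Controls needed for 80% = 1.5 × variance × (z + 0.842)²/0.08². At two-sided 0.10 this is 26.7 for k = 5 and 27.8 for k = 4. The plan's 27/54 is therefore the two-sided calculation with five follow-ups averaged, or nearly so with four. At one-sided 0.10 and k = 5 it would be 19.5, that is 20/40.

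**3. Month-six change.** At 27/54, 0.08/0.0413 = 1.937.
- One-sided 0.10: Φ(1.937 − 1.282) = 74.4% (74.0% by noncentral t). For 80%, 7.2 × 4.508 = 32.5 controls, so 33/66 evaluable.
- 0.05 (half of alpha): 61.5%.
- 0.02 (one fifth of alpha): 45.3%.

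**4. Mean of weeks 12 and 24, one-sided 0.10.** If the full 0.08 is present at both visits: 83.0%. If the difference grows linearly to 0.08 at week 24, it is 0.04 at week 12 and averages 0.06: Φ(0.06/0.0358 − 1.282) = 65%.

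**5. sCD14 power for the week-24 change by family, zinc taken to succeed.**
- Zinc and sCD14: sCD14 is tested at 0.10, so 74%.
- All five, any success: the general bounds are 45% (alpha/5) and 74% (full alpha). With zinc certain, the lowest possible limit is 0.025, which gives 49%. By simulation (1,000,000 runs, Hochberg, correlation 0.3 between marker statistics): 50% if the other three markers are null, 64% if they share sCD14's standardised effect, 70% if theirs is 1.3 times as large. These inputs are assumptions, not in the documents. Varying the correlation from 0 to 0.6 moves the results by 1 point or less. Zinc power of 80% lowers them to 48%, 61% and 67%.
- All five must succeed: joint power cannot exceed 74%. With equal standardised effects and correlation 0.3 it is about 41%.

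**The case against.** The strongest reply is that the 80% is not an error. The sample-size text speaks of post-intervention measurements in the plural and of five measurements, and averaging reproduces its figure. At the stated one-sided 0.10, four averaged follow-ups give 87.9%, and the two scheduled marker visits give 83.0% with a full early effect. This stands. A reader might infer that the trial is shown to be underpowered, but the documents do not support that. They show that contrast and sidedness are not settled.

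A second tempting reading is that the visit-wise Bonferroni is a rival primary rule, or that it multiplies with the step-up correction. No section says to combine them. The visit-wise tests come after the overall comparison of mean curves and include baseline, which cannot be an efficacy test. They are most naturally follow-up comparisons, although the plan should say so.

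Third, week 6 and 18 samples are stored and could be assayed, since the schedule's footnote mentions inflammation markers among possible later uses. So the number of marker visits is a contradiction to reconcile and not a settled two.

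Finally, the 50% to 70% range rests on assumed effects for the other markers. That is correct; only the 45% to 74% bounds follow from the plan's own inputs. None of these replies removes the conflict between five variables and two, or supplies the missing family and success rule.

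**Conclusion.** The point holds. The primary list is inconsistent, the step-up family and success rule are missing, and the same sCD14 result of p = 0.06 passes under one list and fails under the other. That conclusion needs only the Hochberg reading of the step-up rule.

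The power part is narrower. The stated 80% applies to log(sCD14) alone with no alpha split, and it matches two-sided 0.10 with four or five averaged follow-ups. For the month-six change at one-sided 0.10, power is 74% at full alpha and 45% at one fifth, given SD 0.32, correlation 0.85 and 27/54 evaluable. If the full 0.08 is assumed at each averaged visit, the 80% needs lowering only when the week-24 change is made the primary contrast or alpha is split. A slower onset would lower it for the averaged contrast too. Two-sided 0.10 equals a two-way split of one-sided 0.10, so a reader might suppose that a split was built in; the plan does not claim one.

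**What to change.** Before unblinding:

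1. Use one primary list in the objectives, both Co-PRIMARY sections and Statistical Considerations.
2. Next to the step-up rule, name those endpoints as its family and state whether any or all must succeed. The step-up rule can stay; fixed-order testing is not needed, because in a family of zinc and sCD14 it gives sCD14 the same 74% once zinc succeeds.
3. Name one primary contrast, state that the visit-wise tests are supportive, and reconcile the visits at which markers are measured. The mean of weeks 12 and 24 is a sound choice only if the full effect is expected by week 12.
4. In Sample Size and Power analysis, state sidedness and contrast and restate the power. For the week-24 change with zinc succeeding, this is 74% for sCD14 in a family of two. With five and any success it lies between 45% and 74%, with the assumptions for any narrower range given. If all five must succeed, give the joint power.

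The cost is wording only, with no added subjects or visits. The drawback is that either three markers lose co-primary status and the primary objective is reworded, or the stated power falls.

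### Model (1) forces a straight-line zinc effect over weeks, so its predicted curves and any visit contrast read from it are biased if the effect plateaus or fades

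*Combined protocol and SAP*

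**What the plan says.** All of this stands in the protocol's Statistical Considerations unless another section is named.

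- **Purpose.** "Linear mixed-effects modeling will be used in analyzing these longitudinal measurements to understand their trajectories over the study period". Predicted values are to be shown over time, next to summary statistics.
- **Time variable.** T is defined "to be the week when the response measurements are collected from subject" i, so it is numeric. Model (1) contains an arm term (beta1), a linear week term (beta2), one arm-by-week product (beta3), and a random intercept and random linear slope. It has no visit factor, quadratic term or spline.
- **Use of the model.** "From the fitted model (1), we will delineate the predicted outcome variables, association between outcomes and zinc supplementation therapy".
- **Tests.** "Likelihood ratio tests will be used to compare overall mean curves for the two-group". Then: "Tests for inequality in 2-group at baseline (0), 6, 12, 18, and 24 weeks will be performed with multiple testing corrections". The model behind the visit tests is not named.
- **Fallbacks.** The pattern-mixture model for heavy missingness assumes model (1). Generalized estimating equations are a reluctant fallback if parametric assumptions fail. Neither is given a different mean structure.
- **Visits.** The main outcomes "will be measured at baseline (0), 6, 12, 18, and 24 weeks". The schedule under Design and Outcomes shows zinc and the inflammation markers on study only at entry and weeks 12 and 24. The visit procedures and the box plots in the correlational paragraph agree with that schedule.

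**The concern.** The plan asks for trajectories, predicted curves and group comparisons visit by visit. Under model (1) the arm difference can only be beta1 + beta3*t. That is correct only if the difference changes at a constant rate from entry to week 24.

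Nothing in the documents supports a constant rate. Correcting a deficiency could level off. Participants taken off study drug stay in follow-up and are analysed by intent to treat, which could bend the difference the other way.

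If the true difference is curved, the line misstates it at every one of the three visits. Because the line must also pass near week 0, some of the treatment effect is absorbed into beta1. It would then be reported as a baseline difference between arms that randomisation makes zero in expectation.

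**Working it through.** **Inputs.** From the plan: the form of model (1); visits 0/12/24 (schedule) or 0/6/12/18/24 (statistical text); SD 0.32 for log(sCD14), correlation 0.85, difference 0.08, and 27 control and 54 zinc participants evaluable. Assumed by me: the shapes of the true effect, and complete on-schedule data unless stated.

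**The plan's own figure.** The change method gives SD = 0.32*sqrt[(1+(r-1)*0.85)/r + 1 - 2*0.85] for one baseline and r follow-ups. With r = 5 and two-sided 0.10, SD = 0.136 and the result is 27/54 (power 0.804). With r = 4 it is 28/56. The stated one-sided 0.10 gives 20 to 21 controls for these designs.

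**Three visits.** For balanced complete data, generalized least squares with a random intercept and slope gives the same line as ordinary least squares. Let c = d0 - 2*d12 + d24. The errors of the line at weeks 0, 12 and 24 are -c/6, +c/3 and -c/6.

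| True difference (0, 12, 24) | c | Fitted by model (1) | 24*beta3 |
|---|---|---|---|
| 0, D, D | -D | 0.17D, 0.67D, 1.17D | D |
| 0, D, D/2 | -1.5D | 0.25D, 0.50D, 0.75D | 0.5D |

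With D = -0.08 in log(sCD14), the plateau is fitted as -0.013, -0.053 and -0.093, against a truth of 0, -0.080 and -0.080.

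**What beta3 estimates.** Its visit weights are (-1, 0, +1)/24. So 24*beta3 equals the arm difference in change from baseline to week 24, whatever the curve, and week 12 has zero weight in that point estimate.

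**Five visits.** The slope weights are (-1/30, -1/60, 0, 1/60, 1/30). For a plateau from week 6, (0, D, D, D, D):
- beta3 = D*(-1/60 + 0 + 1/60 + 1/30) = D/30, so 24*beta3 = 0.8D.
- The mean difference, located at week 12, is 0.8D. The fitted values are 0.8D - 12*D/30 = 0.4D at baseline, 0.8D at week 12 and 1.2D at week 24.

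On this schedule 24*beta3 is also wrong, by 20%.

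**Which week-24 contrast to use.** The effective size is 1/(1/27 + 1/54) = 18. Power at one-sided 0.10 is Phi(0.08/SE - 1.282):

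| Contrast | Variance per participant | SE | Power |
|---|---|---|---|
| Raw week-24 difference | 0.32^2 = 0.1024 | 0.0754 | 0.41 |
| Change to week 24 | 0.1024*2*(1-0.85) = 0.0307 | 0.0413 | 0.74 |
| Baseline constrained equal | 0.1024*(1-0.85^2) = 0.0284 | 0.0397 | 0.77 |

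**Cost if the effect is truly linear.** I assume equal correlations and no slope variance. With three visits, 24*beta3 is the change contrast, so power is the same 0.74. With five visits the variance of 24*beta3 is 24^2*0.15*0.1024/360 = 0.0246, SE = sqrt(0.0246/18) = 0.0370, and power is 0.81.

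**The case against.** - **The sized effect may be untouched.** The sample size refers to change from baseline at month six. On the 0/12/24 schedule with complete data, 24*beta3 estimates exactly that. This stands. A reader might infer that the month-six result itself is biased. That holds only if beta1 + beta3*24 is reported as the week-24 effect, or if five visits are fitted.
- **The visit tests may be separate.** The plan does not say that they are contrasts from model (1). Separate tests at each visit would escape the bias, and plotted summary statistics would show a misfit. This stands too: the tests are unspecified, not shown to be wrong. The predicted curves and the treatment association are explicitly taken from model (1) and do not escape.
- **Week 12 is not wasted.** From the zero weight, a reader might infer that week 12 contributes nothing. The documents do not support this. The named test compares overall mean curves, and week 12 enters it through beta1. Week 12 also enters the standard errors: in one simulated fit, shifting the zinc arm's week-12 values by -0.2 left the slope at -0.0522 per 12 weeks but moved its standard error from 0.0253 to 0.0281. With 15% of week-24 values missing, week 12 cuts the variance of beta3 by about 3.4% to 4.5%, depending on the assumed slope variance and visit timing. A week-24 contrast in a visit-factor model likewise gives week 12 no direct weight with complete data.
- **A line is efficient if true.** This stands, mainly for five visits.

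**Conclusion.** The point holds in a limited form. The mean structure of model (1) is a straight line in weeks, and no stated fallback changes it. If the effect plateaus by week 12, a week-12 effect read from the fitted line is 33% too small, the week-24 effect is 17% too large, and D/6 appears at baseline. If it halves by week 24, the week-24 reading is 0.75D against a true 0.50D. With five visits and a plateau from week 6, the false baseline difference is 0.4D.

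These sizes depend on the assumed shapes and on complete, on-schedule data. The documents do not show that the effect will curve; they also give no reason to rule it out. If the effect is linear there is no bias. The change should be made because it is cheap, settles where the visit tests come from, and ties the analysis to a named week-24 effect.

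**What to change.** 1. Replace the linear week terms in model (1) with visit as a factor and arm-by-visit terms, with an unstructured within-participant covariance in place of the random intercept and slope.
2. Use the visits at which each outcome is actually measured. Reconcile weeks 0/6/12/18/24 in the statistical text with 0/12/24 in the schedule and the correlational paragraph.
3. Name the primary contrast at week 24 so that it uses baseline: either the arm difference in change from baseline, or the week-24 difference with arm means constrained equal at baseline. An unconstrained raw week-24 difference should not be used, because its power is about 0.41 at 27/54.
4. Report week 12, the predicted curves and all visit tests from this same model, and say so.

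The cost is SAP wording and a few more parameters, which 93 to 95 participants support. If the effect is truly linear, the loss against a slope model is nil for the change contrast with three complete visits, and about 0.74 against 0.81 with five. At 27/54 neither baseline-using contrast reaches 0.80 under the stated inputs, so the power statement should be rechecked against whichever contrast is named.
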